4 STATISTICAL METHODOLOGY

4.1 Data Set Descriptions

A summary of all patient data will be kept in a study database developed for this study. In addition to the experimental data, this database will include recipient and donor demographics and transplant relevant medical history (comorbidities, HLA type, etc.), graft function, immunosuppressive medications and levels, and a running summary of the patient's post transplant course. Data will be recorded and reported in accordance with the standards required by the United Network for Organ Sharing (UNOS). The data set will consist of all patients who are randomized and transplanted and will be used for all

efficacy analyses. The as-treated data set will consist of all patients who receive at least one dose of belatacept and will be used for all safety analyses. Subgroup analyses will be performed for selected endpoints in subjects whom withdrawal was attempted and not attempted in order to provide supporting information to the main analyses. Demographic and baseline characteristics of patients will be summarized descriptively by treatment group, by means and standard deviations (SDs) for continuous variables and frequency distribution for categorical variables. Summaries will be performed based on the data set.

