6.2 Maintenance Immunosuppressive Reduction

Beginning any time after year 1 (week 53), participants who are deemed eligible for sirolimus withdrawal as determined by clinical and flow cytometric parameters

(described below) may be withdrawn from sirolimus. Withdrawal will proceed at a maximum rate of 66% of the original dose for 4 weeks, 33% of the original dose for another 4 weeks, then discontinued. However, each reduction in dose will be predicated on stable flow cytometric profile.

Criteria for Sirolimus Withdrawal. Participants will be deemed eligible for withdrawal of sirolimus if they meet all of the following criteria:

1. No episodes of steroid resistant acute rejection since transplant, and no episodes of steroid sensitive rejection for 12 months.
2. Stable renal function, as defined by both of the following:
 - a. GFR, using calculated CrCl (Cockcroft-Gault) of > 40ml/min.
 - b. Creatinine, which in the 12 weeks preceding withdrawal has not increased more than 20% with respect to the lowest creatinine observed during the same period.
 - c. Absence of histologic evidence of acute or chronic rejection on pre-withdrawal renal biopsy according to the Banff criteria for acute, chronic and humoral rejection.
3. Absence of DSA reactivity, as measured by de novo anti-donor-HLA antibodies.
4. ALC at least 80% of the baseline ALC prior to alemtuzumab.
5. Ki67 expression on CD3+ T cells that is within 1 standard deviation of the normal expression in untreated controls. Ki67 is typically seen in <3% of lymphocytes in health controls and a value >5% exceeds the value accepted for purposes of this trial.

For determining eligibility, a renal biopsy will be obtained and creatinine clearance will be estimated. Requisite blood samples will be obtained within two weeks before starting sirolimus withdrawal. Results of laboratory assessments of immune status will be made available to, and reviewed by, the investigator. These data will be reviewed with the knowledge of previous results of immunosuppression withdrawal obtained in the current trial up to the time of review.

Maintenance Immunosuppressive Therapy

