| BK viremia/viruria PCR | | X | | | X |
| Adverse Events | X | X | | | X |
| QoL | | | | X | |
| Neurologic Exam | | | X | | |
| Immunogenicity | | | | X ^a | |

^a These are specific study related assays for reporting purposes.

Long-Term Follow-Up Cohort 1

| Tests / Evaluations | Every 6months | Yearly |
|----------------------------------------------------------------------|----------------------|----------------|
| Telephone Reporting | X | |
| Serum Chemistry/ lipids /CBC | X | |
| Sirolimus trough | | X |
| Lymphocyte subsets | X | |
| Peripheral transcription | | X |
| CMV and EBV PCR | X | |
| BK viremia/viruria PCR | X | |
| PRA | | X |
| Anti-Donor Antibody | | X |
| Donor-specific and third party mixed lymphocyte responsiveness/ ICCS | | X |
| Renal Biopsy | | X ^b |
| Intragraft mRNA Analysis | | X ^b |
| Adverse Events | X | X |
| QoL | X | |
| Neurologic Exam | X | |
| PK | | |
| Immunogenicity | X | |

=

^b To be performed prior to weaning patient to monotherapy (generally at 12 months) and again after stable on monotherapy as clinically indicated.

Long-Term Follow-Up Cohort 2

| Tests / Evaluations | Monthly after Year 1 | Every 3 months from 6 - 24Months | Every 6 months | Yearly |
|----------------------------------------------------------------------|-----------------------------|-----------------------------------------|-----------------------|----------------|
| Telephone Reporting | | | X | |
| Serum Chemistry/ lipids /CBC | X ^c | | X | |
| Sirolimus trough ^d | X | | | X |
| Lymphocyte subsets Ki67 | | | X | |
| Peripheral transcription | | | | X |
| CMV and EBV PCR | | X | X | |
| BK viremia/viruria PCR | | X | X | |
| PRA | | | | X |
| Anti-Donor Antibody | | | | X |
| Donor-specific and third party mixed lymphocyte responsiveness/ ICCS | | | | X |
| Renal Biopsy | | | | X ^b |
| Intra-graft mRNA Analysis | | | | X ^b |
| Adverse Events | X ^e | | | |
| QoL | | | X | |
| Neurologic Exam | | | X | |
| Immunogenicity | | | X | |

^cStudy participants may have these labs drawn more or less frequently as deemed clinical necessary by the investigator.

^dStudy participants who are not weaning sirolimus and are on a stable, low dose can have trough levels monitored as frequently as a monthly basis or as clinically indicated.

^eIf study participant is on a stable dose of sirolimus, not weaning, and receiving commercial belatacept as an outpatient, then adverse events may be assessed every three months.

Year 1 Medication Flowchart

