| | Day of Transplant 1 st Dosing Day 1 | Day 2 | Day 4 | Day 8 | Day 14 | Mo 1 | | | | Mo 3 | | | | Mo 6 | | | | Mo 12 | | |
|------------------------------|-------------------------------------------------------------------------------------------------------------------------------------------------------------------------------------------------------------------------------------------------------------------------------------------------------------------------------------------------------------------------------------------------------------------------------------------------------------|-------|-------|-------|--------|------|------|------|-------|-------|-------|-------|-------|-------|-------|-------|-------|-------|-------|-------|
| | | | | | | Wk 4 | Wk 6 | Wk 8 | Wk 10 | Wk 12 | Wk 16 | Wk 20 | Wk 24 | Wk 28 | Wk 32 | Wk 36 | Wk 40 | Wk 44 | Wk 48 | Wk 52 |
| | | | | | Wk 2 | | | | | | | | | | | | | | | |
| belatacept 10 mg/kg | X | | X | X | X | X | X | X | X | X | X | X | X | | | | | | | |
| belatacept 5 mg/kg | | | | | | | | | | | | | | X | X | X | X | X | X | X |
| sirolimus | Sirolimus will be started on post-op day 1 at a dose of 2 mg per day orally. Doses will be adjusted to maintain 24-hour trough levels of 8-10 ng/ml until the drug is weaned as described below. | | | | | | | | | | | | | | | | | | | |
| methylprednisolone 500 mg | X | | | | | | | | | | | | | | | | | | | |
| alemtuzumab 30 mg | X | | | | | | | | | | | | | | | | | | | |
| Prophylaxis | Post-operative viral (oral valganciclovir of duration in keeping the standard of care based on pre-operative donor and recipient CMV status), fungal (oral nystatin or clotrimazole), and bacterial prophylaxis (perioperative surgical prophylaxis transitioning to oral Pneumocystis prophylaxis) dosed for 6 months post transplantation. All prophylaxis agents will be withdrawn at 6 months unless there are specific clinical indications otherwise. | | | | | | | | | | | | | | | | | | | |
| Immunosuppression Withdrawal | During year 2 (weeks 53-104), weaning of immunosuppression will begin for all patients meeting pre-defined criteria. Patients will be first weaned off sirolimus over at least a 2 – 6 month period. After sirolimus, is weaned, patients will remain on belatacept monotherapy indefinitely. | | | | | | | | | | | | | | | | | | | |

9 Details of Research Procedures

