9.2 Post-transplant Monitoring

Post-transplant Blood Monitoring. In general, functional monitoring will proceed in keeping with the standard of care for kidney transplantation at the Emory Transplant Center. Blood for testing of renal function (creatinine, BUN, hemoglobin/hematocrit) and electrolytes (including sodium, potassium, chloride, bicarbonate, magnesium, calcium and phosphorous) will be drawn daily until discharge and at least two times weekly for one month. Patients will be monitored weekly for at least 3 months or until the ALC exceeds 500 cells/mm³, whichever is longer. Thereafter, renal function will be assessed at least every two weeks until they reach their one-year evaluation. Lymphocyte repopulation and specific Ki67 and T_{REG} and B_{TRANS} phenotypes will be assessed monthly until 1 year after sirolimus elimination, and then every 3 months through 5 years by analysis of 7ml of heparinized blood by flow cytometry.

Biopsy Monitoring. A protocol biopsy will be performed following allograft reperfusion. Additional protocol biopsies will be performed at 6 months, and when the criteria for weaning to monotherapy belatacept are met (generally this will be during the second post transplant year) and again when the patient has been weaned to monotherapy belatacept for three months. An additional biopsy will be performed one year after weaning off sirolimus. It is assumed that histological acute allograft rejection is indicative of under-immunosuppression. Since histological rejection has been documented to occur in the absence of clinical renal dysfunction (so-called sub-clinical rejection) in up to 30% of persons with stable allograft function, it is reasonable to assume that some patients studied in this trial will have sub-clinical rejection, and thus be inappropriate for further immunosuppressive reduction. Protocol biopsies are thus clinically indicated to pre-empt inappropriate immunosuppressive weaning, as well as to detect other occult pathology

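### Do the supportive summaries by withdrawal attempted or not attempted (Section 4.1) need their endpoints and time origin written into the plan?

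*Combined protocol and SAP*

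**What the plan says.** Section 4.1 uses the set of transplanted patients for all efficacy analyses and then adds: "Subgroup analyses will be performed for selected endpoints in subjects whom withdrawal was attempted and not attempted". The purpose given is to support the main analyses. Neither 4.1 nor 4.2 lists the endpoints, defines an attempt, or gives a time origin for this split.

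Other sections do give origins, endpoint by endpoint. Section 2.2 counts rejection and chronic allograft nephropathy at 1, 3 and 5 years from transplant. Sections 2.1 and 4.2 count the primary endpoint from the end of sirolimus. Section 4.2 plans no hypothesis test for the primary endpoint and describes the efficacy analyses as generally descriptive.

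Entry to the attempted group is set in Section 6.2. Timing: "Beginning any time after year 1 (week 53), participants who are deemed eligible for sirolimus withdrawal"; the medication flowchart in 8.1 says "During year 2 (weeks 53-104), weaning of immunosuppression will begin for all patients meeting pre-defined criteria". Rejection: "No episodes of steroid resistant acute rejection since transplant, and no episodes of steroid sensitive rejection for 12 months". Stable renal function, a pre-withdrawal biopsy free of rejection and absence of donor-specific antibody are also required.

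Section 9.2 schedules a biopsy "again when the patient has been weaned to monotherapy belatacept for three months" and adds: "An additional biopsy will be performed one year after weaning off sirolimus". Footnote b in 8.1 words the post-monotherapy biopsy differently: "again after stable on monotherapy as clinically indicated".

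**The concern.** Group membership is fixed by events after transplant, so splitting transplant-origin endpoints by it builds in a difference.

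- Withdrawal starts after week 53, so nothing in a 1-year row can be an effect of withdrawal.
- Death, graft loss or steroid-resistant rejection before withdrawal can be counted only in the group not attempted. The attempted group is free of death and graft loss up to its start date by definition.
- The biopsies that 9.2 schedules after weaning are done only in weaned patients. They can raise detected rejection in that group, which pushes the other way.
- Patients converted from sirolimus to MMF may still be considered for weaning (6.1), but 4.1 does not say which group they join.

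What would be at stake is a misreading. A reader could take a gap between the columns, or the lack of one, as evidence about withdrawal when it reflects eligibility rules and the biopsy schedule.

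**Working it through.** **Planning figures (3.1, 3.4).** N = 20. Pre-withdrawal rejection: 0.20 × 20 = 4. Other non-attempts: 4. Attempted: 20 − 4 − 4 = 12. Successes: 12 × 0.50 = 6. These reproduce the plan's 12 and 6.

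**Size of the artefact if events are counted from transplant**

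- *Rejection before withdrawal.* At 3.4's upper limit: not attempted 4/8 = 50% (exact 95% CI 15.7 to 84.3%), attempted 0/12 = 0% (0 to 26.5%). With one such rejection, the first-year clinical count that 3.4 reports from earlier experience: 1/5 = 20% against 0/15.
- *Graft loss.* Section 1.2 gives one-year graft survival above 92% (deceased donor) and 96% (live donor). With 10 of each (assumed), expected first-year losses are at most 10 × 0.08 + 10 × 0.04 = 1.2. A single loss among the eight reads 1/8 = 12.5% against 0/12.
- *Event-free time.* A start in weeks 53 to 104 guarantees 52 to 103 weeks free of death and graft loss: 52/156 = 33% to 103/156 = 66% of a 3-year window, and 52/260 = 20% to 103/260 = 40% of a 5-year window.

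**Simulation with no effect of withdrawal.** The assumptions are not in the documents: constant hazards, 20% first-year rejection, 2% a year afterwards, any earlier rejection bars an attempt, 75% of event-free patients attempt, and start dates are uniform over the year from week 53. Three-year rejection counted from transplant is 2.9% attempted against 52.8% not attempted. Counted from week 53 among event-free patients it is 2.9% against 6.8%. A week-53 start therefore removes most of the gap but not all, because events between week 53 and the attempt still fall in the other column.

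**Direction for rejection once withdrawal failures are included**

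- Four pre-withdrawal rejections: if none of the attempted reject, 0% − 50% = −50 points; if all six failures are rejections, 6/12 − 4/8 = 0.
- One pre-withdrawal rejection: if none of the attempted reject, 0% − 20% = −20 points; if half do, 50% − 20% = +30 points.

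The sign is not fixed.

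**Extra detection by biopsy.** Section 9.2 puts subclinical rejection at "in up to 30% of persons with stable allograft function". One biopsy in all 12 would find at most 12 × 0.30 = 3.6. That is a ceiling: these patients have just passed a rejection-free biopsy, and some may not complete the taper and so may not reach the post-weaning biopsies. The excess is nil if the wording in 8.1 means that no biopsy is scheduled after weaning. The documents do not fix an amount.

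**What depends on the split.** The primary analysis uses the full efficacy set: 6/20 = 30% on the planning figures. The split adds 6/12 = 50%, the quantity on which 3.4 is based. Neither number uses a comparison of the two groups from transplant.

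**The case for a change.** The best case for amending the plan is this. Transplant is the only origin that 2.2 gives for rejection and chronic allograft nephropathy, so it is the natural default. The tables are offered as support in a non-randomised study, and readers will compare adjacent columns whatever the label says. Leaving the endpoints open also allows them to be picked after the data are seen. A sentence or two would settle it.

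Part of this stands. The non-comparability is real for those endpoints and can be large, and descriptive status does not remove it. It does not carry the conclusion, for three reasons.

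- Section 4.1 plans summaries within each group and specifies no contrast. Some endpoints fit the split well: the success proportion, and the donor-specific responses that 9.2 times at the start of withdrawal and three months after it.
- With about 8 and 12 patients, the intervals above already warn against reading much into a gap.
- Tighter wording is not automatically better. Ending pre-withdrawal follow-up at the first dose reduction leaves no end date for patients who never have one. A category for patients no longer on sirolimus could label an MMF wean as not attempted. Replacing the sentence outright would lose the attempted-only success proportion.

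The reversal of direction should not be pressed through requalification of earlier rejecters. Section 6.2 allows it after a steroid-sensitive episode, but 3.4 counts pre-withdrawal rejecters as excluded, and 1.1 speaks of patients rejection-free for one year. Those statements, and the biopsy wording in 9.2 and 8.1, must be reconciled. That is a separate matter from the subgroup sentence.

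**Conclusion.** The observation is correct, but it does not call for a change. Section 4.1 leaves the endpoints and time origin of a supportive, descriptive split unwritten. If transplant-origin endpoints were put into it, the artefact could reach 50% against 0% for pre-withdrawal rejection at 3.4's upper limit, and 20% against 0% with a single such rejection. That rests on N = 20, four other non-attempts and no earlier rejecter being withdrawn. The primary proportion and its exact confidence interval are untouched, and no test or between-group estimate is planned.

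An analyst laying out these tables would ordinarily report transplant-origin endpoints for the whole cohort, use the split for the success proportion among attempted patients, list the others by reason, and note where a converted patient has been placed. The present wording permits all of that.

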4.2 Analyses

Demographics and Baseline Characteristics

Demographic and baseline characteristics of patients will be summarized descriptively by treatment group, by means and standard deviations (SDs) for continuous variables and frequency distribution for categorical variables. Summaries will be performed based on the data set.

Efficacy Analyses

No formal statistical hypothesis testing will be performed for the primary endpoint. All efficacy analyses will generally be descriptive in nature. The primary efficacy analysis will be to assess the proportion of patients successfully withdrawn from sirolimus for one year. The point estimate of this proportion and the exact two-sided 95% confidence interval (CI) will be provided for each treatment group. A patient will be considered to be successfully withdrawn from immunosuppression for one year if the patient has been administered only belatacept for a period of 365 days, following successful completion of sirolimus, and has not experienced biopsy-proven acute rejection, formation of DSA, or graft loss for this same period of 365 days. Secondary efficacy outcome measures involving incidences and proportions will be descriptively summarized with point estimates and exact, two-sided 95% CIs by treatment group. Other secondary efficacy outcome measures will be descriptively summarized by means and SDs for continuous outcomes and frequency distributions for categorical outcomes.

Safety Analyses

All AEs and SAEs will be summarized by treatment group. Laboratory values will also be descriptively summarized.

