Protocol Title: Use of Belatacept during Post Depletional Repopulation to Facilitate Tolerance in Renal Allograft Recipients

Investigator: [name]

Protocol Date: 10Jul2015

NCT Number: NCT00565773

SYNOPSIS

| |
|-----------------------------------------------------------------------------------------------------------------------------------------------------------------------------------------------------------------------------------------------------------------------------------------------------------------------------------------------------------------------------------------------------------------------------------------------------------------------------|
| Title of Study: Use of Belatacept During Post Depletional Repopulation to Facilitate Tolerance in Renal Allograft Recipients |
| Study Phase: II |
| IND Sponsor: [name] PhD |
| Participating Site: Emory University |
| Study Design: Single-center, open-label, proof-of-concept study in non-HLA-identical live and deceased donor renal transplants. |
| Duration of Study: Subjects will be enrolled over a one-year period and followed for up to five years. |
| Number of Subjects: Approximately 40 |
| Study Population: Adult, EBV seropositive patients who do not have evidence of DSA pretransplant and who are scheduled to receive a kidney transplant at Emory University. Candidacy for transplantation will be determined using the standard methods of evaluation active at Emory during the study period. |
| Primary Objective: To determine whether lymphocyte depletion with alemtuzumab followed by belatacept and sirolimus will permit renal allograft function without rejection, and will allow for a general population of renal transplant recipients to be weaned to belatacept monotherapy for maintenance immunosuppression. The primary endpoint will be the number of patients successfully withdrawn from sirolimus for 1 year after their last dose of sirolimus. |

Secondary Objectives:

- 1) Determination of the prognostic ability of assays based on surface phenotype changes seen during homeostatic repopulation, including Ki67 expression, T_{REG} and B_{TRANS} cell surface phenotypes, and T_M to T_{REG}/B_{TRANS} balance, with regard to the anticipation of successful immunosuppressive drug withdrawal.
- 2) Assessment of the proposed therapies to prevent biopsy proven acute rejection at 1, 3 and 5 years post-transplant compared to the standard reported in the SRTR database for similar patients.

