2.2 Secondary Objectives

1. Determination of the prognostic ability of assays based on surface phenotype changes seen during homeostatic repopulation, including Ki67 expression, T_{REG} and B_{TRANS} cell surface phenotypes, and T_M to T_{REG}/B_{TRANS} balance, with regard to the anticipation of successful immunosuppressive drug withdrawal.
2. Assessment of the proposed therapies to prevent biopsy proven acute rejection at 1, 3 and 5 years post-transplant compared to the standard reported in the SRTR database for similar patients;
3. Assessment of the incidence of biopsy proven chronic allograft nephropathy at 1, 3 and 5 years post-transplant compared to that reported in the SRTR database for similar patients;
4. Assessment of the composite of occurrence of malignancies, and opportunistic infections by 1, 3 and 5 years compared to that reported in the SRTR database for similar patients;
5. Long term assessment of donor-specific immune responsiveness after prolonged therapy with belatacept (with or without sirolimus), and during and following drug

- withdrawal as determined by in vitro alloresponsiveness in CFSE mixed lymphocyte reactivity and ICCS;
6. Characterization of the repopulating immune system with regard to cell surface phenotype using MFC compared to prior experience with alemtuzumab alone or combined with other related regimens; and,
 7. Comparison of the function and survival of allografts transplanted using this protocol to historical controls transplanted using conventional immunosuppression to establish an initial assessment of this approach in a general transplant population.

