3 STUDY DESIGN AND EVALUATION

3.1 Study Design

This will be a single-center, open-label, non-randomized, proof-of-concept study in recipients of living or deceased donor renal transplants (DDRTs). Twenty renal transplant patients will be enrolled, at least 10 of which will be recipients of DDRTs. At the time of transplantation, participants will be given alemtuzumab, 30mg intravenously over three hours. Participants will receive combination maintenance therapy with sirolimus and belatacept for at least one year. Patients' absolute lymphocyte counts (ALCs) and percent expression T cell of Ki67 will be assessed monthly. After one year of therapy, participants may consent to and begin sirolimus withdrawal or continue therapy through study close. Patients wishing to withdraw from sirolimus will begin sirolimus weaning when their ALC has reached at least 80% of baseline and had two consecutive monthly assessments of their percent expression of Ki67 fall within at least one standard deviation of the Ki67 expression of a healthy control population. Weaning will be triggered of the Ki67 expression, with other surface phenotype assessments being followed observationally. Patients meeting these parameters will be weaned off of sirolimus by halving the dose and/or increasing the dosing interval over at least a three-month period. Each dose reduction will require stable (within 1 standard deviation) peripheral Ki67 expression. After sirolimus is discontinued, patients will remain on belatacept monotherapy indefinitely. Clinical and mechanistic observation will continue for the duration of the study to assess the efficacy and safety of this approach. Subjects will be followed for at least five years.

Duration of Study

Subjects will be followed for at least five years. Belatacept is now approved by the FDA. Therefore, subjects remaining on belatacept at the conclusion of their five-year participation would be eligible to continue this therapy. If at the conclusion of this study belatacept is not commercially available to patients, the Principal Investigator will discuss other treatment options utilizing approved immunosuppressive therapies with the subject. If subjects are successfully weaned from sirolimus as a result of their participation in this protocol, there will be no need for consideration of alternative therapy.

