3.3 Criteria for Evaluation

1. Number of patients successfully withdrawn from sirolimus for 12 months after last dose of sirolimus
2. Biopsy proven acute rejection or chronic allograft nephropathy by 1, 3 and 5 years
3. Evidence of donor-specific hyporesponsiveness by MLR and ICCS
4. Evidence of regulatory T cell and transitional B cell activity in the periphery and allograft
5. Donor specific and third party alloantibody formation

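### The 1-, 3- and 5-year incidences are planned as crude proportions with no rule for incomplete follow-up, which can understate late rejection and chronic allograft nephropathy

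*Combined protocol and SAP*

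**What the plan says.** Section 2.2 sets outcomes at fixed times after transplant, beginning with "biopsy proven acute rejection at 1, 3 and 5 years post-transplant compared to the standard reported in the SRTR database". It does the same for chronic allograft nephropathy and for the composite of malignancy and opportunistic infection. Section 3.3 repeats the first two: "Biopsy proven acute rejection or chronic allograft nephropathy by 1, 3 and 5 years".

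The method in section 4.2 is one sentence: "Secondary efficacy outcome measures involving incidences and proportions will be descriptively summarized with point estimates and exact, two-sided 95% CIs by treatment group". The same section says "No formal statistical hypothesis testing will be performed for the primary endpoint", and that efficacy analyses are generally descriptive. The denominator comes from section 4.1: "The data set will consist of all patients who are randomized and transplanted and will be used for all" efficacy analyses. The current design is not randomized, so I read this as all transplanted patients.

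On length of follow-up, the synopsis says "Subjects will be enrolled over a one-year period and followed for up to five years", while section 3.1 says "Subjects will be followed for at least five years".

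Sections 6.4 and 6.8 list reasons for stopping belatacept or leaving the study, and give 8 weeks of safety follow-up after discontinuation. Section 11.6 requires death, graft loss, malignancy, PTLD and serious infection to be reported to the end of the study whether or not drug was stopped. Rejection and nephropathy are not on that list.

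The available text has no Kaplan-Meier or cumulative-incidence estimate, no number at risk, and no rule for a patient who does not reach 1, 3 or 5 years.

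**The concern.** A proportion of all transplanted patients with an exact binomial interval estimates a 3- or 5-year incidence correctly only if each patient's status at that time is known. The plan has a route by which it will not be: a patient leaves study therapy, has 8 weeks of safety follow-up, and no later collection of rejection or nephropathy is required. Such a patient adds one to the denominator and can add nothing to the numerator.

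At stake are the late rejection and nephropathy figures, which are to be set beside registry rates. The rule for incomplete follow-up is also open. With no rule written down, the choice between keeping and dropping these patients could be made after the data are seen.

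**Working it through.** **1. The plan's own figure.** No size or precision is stated for the 1-, 3- and 5-year incidences. The only sample-size figure is in section 3.4, and it reproduces from the 20 patients of section 3.1: 20 − 0.20 × 20 − 4 = 12 attempted withdrawals, and 12 × 0.50 = 6 successes. The synopsis gives about 40 patients, so I use both 20 and 40.

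**2. The unstated rule.** Suppose 4 of 20 patients have an event and 4 others leave early without one. The 4 early leavers are an assumption. Exact limits are the beta quantiles Beta(0.025; x, n − x + 1) and Beta(0.975; x + 1, n − x).

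| Handling | N = 20 | N = 40 (doubled) |
|---|---|---|
| Kept in | 4/20 = 20.0% (5.7 to 43.7) | 8/40 = 20.0% (9.1 to 35.6) |
| Dropped | 4/16 = 25.0% (7.3 to 52.4) | 8/32 = 25.0% (11.5 to 43.4) |

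At N = 20 the widths are 43.7 − 5.7 = 38.0 points and 52.4 − 7.3 = 45.1 points. Keeping the early leavers gives the narrower interval because it treats them as fully observed.

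Now put the same patients in time order: 2 events in year 1, then 4 leave, then 2 late events. Kaplan-Meier gives 1 − (18/20) × (13/14) × (12/13) = 22.9%, between the two crude answers.

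**3. Size of the shortfall if patients are kept in.** The documents give no loss rate, so I assume one. Let p be the true 5-year incidence and c the fraction lost by year 5, with constant and independent hazards. Write a = −ln(1 − p) and b = −ln(1 − c). Then

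crude 5-year proportion = a/(a + b) × [1 − (1 − p)(1 − c)].

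For p = 0.20 and c = 0.40: a = 0.2231, b = 0.5108, so 0.3040 × (1 − 0.48) = 0.158.

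| Lost by year 5 (assumed) | True 20% reads | True 30% reads |
|---|---|---|
| 0% | 20.0% | 30.0% |
| 10% | 19.0% | 28.6% |
| 20% | 18.0% | 27.1% |
| 30% | 16.9% | 25.5% |
| 40% | 15.8% | 23.8% |
| 50% | 14.6% | 22.1% |

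**4. Earlier times.** For a true 5-year incidence of 20% with 20% lost, the 3-year figure reads 11.7% against a true 12.5%. At 1 year the largest gap in the range examined (true 5-year incidence up to 30%, loss up to 50%) is 6.9% read as 6.4%, which is 0.5 points.

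**5. Dependence on the hazard shape.** Suppose half the patients are seen for only 3 years and the true 5-year incidence is 20%.
- Constant hazard: 3-year incidence is 1 − 0.80^(3/5) = 12.5%, so the crude figure is 0.5 × 20 + 0.5 × 12.5 = 16.3%.
- 80% of events in year 1, the rest even over years 2 to 5: 3-year incidence is 20 × (0.8 + 0.2 × 2/4) = 18%, so the crude figure is 0.5 × 20 + 0.5 × 18 = 19.0%.

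The plan does not settle which shape applies. Section 3.4 allows up to 20% rejection before withdrawal starts, which points to early events. Withdrawal itself begins only after year 1, which makes later events plausible.

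**The case against.** The strongest reply is that this is an omission and not a stated error. No sentence says that patients with short follow-up count as event-free. A reader might infer such a rule from sections 4.1 and 4.2, but those name only an analysis set and a summary. Dropping the patients is equally open and moves the figure the other way. That stands, so the shortfall is conditional on keeping them in.

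Other stronger readings are tempting, and the documents do not support them:

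- *The synopsis and section 3.1 disagree, so follow-up will be short.* The two statements conflict, but the conflict creates no missing time. Section 3.1 speaks of five-year participation and section 9.2 of monitoring through 5 years, and no closing date before year 5 is stated. The firmer source of incomplete data is sections 6.4 and 6.8.
- *All the landmark outcomes are equally affected.* Section 11.6 largely protects malignancy, serious infection and graft loss after drug is stopped. The exposure is mainly rejection and nephropathy, and perhaps opportunistic infections that are not serious.
- *Deaths make the crude proportion wrong.* With death as a competing event and no other censoring, cumulative incidence equals the crude proportion. Only loss of observation matters.
- *Five-year graft survival is a crude landmark in this plan.* Objective 7 compares graft function and survival with historical controls but names no times.
- *The bias favours the regimen against the registry.* Keeping patients in lowers the trial's side. The documents do not say how the registry rates are computed, so the net direction is not established.

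It is also fair that a 2-point shift at 20% loss is small beside an interval of 5.7% to 43.7%, and that no test or decision hangs on these outcomes.

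**Conclusion.** The point holds in a limited form. For rejection and nephropathy at 3 and 5 years, the plan pairs a full denominator with collection that may stop 8 weeks after study therapy ends, and it gives no censoring rule. Applied literally, that understates late incidence and gives an interval that is too narrow.

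Under a constant hazard with 10% to 40% lost by year 5, a true 20% reads about 19.0% to 15.8%, and a true 30% about 28.6% to 23.8%. The effect is smaller if most events come early, and at most about 0.5 points at year 1. The loss rates and hazard shape are my assumptions. The shift is modest beside the interval width at 20 to 40 patients, and the outcomes are secondary and descriptive. It is worth correcting because a better estimator is standard and almost free. The primary endpoint is outside this point.

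**What to change.** In section 4.2, replace the crude summary for the landmark outcomes as follows.

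- Estimate rejection, chronic allograft nephropathy and malignancy or opportunistic infection at 1, 3 and 5 years by cumulative incidence. Treat death as a competing event, and graft loss as well for rejection and nephropathy.
- Estimate graft and patient survival by Kaplan-Meier.
- Give 95% confidence intervals and the number at risk at each time.
- Define the censoring date for each outcome and tabulate reasons for leaving. These estimators assume that leaving is unrelated to later risk, which is doubtful for patients removed for adverse events.
- Note that nephropathy is found only at biopsy, so its timing is approximate.
- Reconcile the synopsis with section 3.1 on length of follow-up.
- Keep the exact binomial interval for the primary endpoint.

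The cost is a few sentences of SAP text and standard code, with no added patients or procedures. The reported incidences may be slightly less favourable and their intervals wider.
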